In another recent fructose restriction/weight loss intervention in middle-aged adults, obese women showed a significant improvement in PWV, while men did not (Figure 4A). Relevant to this proposal, we found that PWV correlated with SUA in women after 4 weeks of weight loss (Figure 4B). TNF α and UA were the only variables that predicted $PWV = 3.604 + (0.270*UA) + (0.132*TNF\alpha)$, $r = 0.712$, $p = 0.0025$ following the weight loss in women, suggesting that SUA is a modifiable risk factor in the development of arterial stiffening in women. In another preliminary study, exposure to high glucose and high UA increased production of inflammatory markers in cultured human aortic endothelial cells

(Figure 5). Data from our basic and human studies complement growing epidemiological evidence that hyperuricemia in women is related to increased arterial stiffness, putting women at a high risk for CVD. We propose that the sexual dimorphism in arterial stiffness associated with T2D is mediated, in part, by sex-dependent effects of UA and XO activation.

B. Summary of Study Objectives

We will accomplish the following specific aims:

Aim 1: To determine if sex-related differences exist in the relationship between SUA levels and arterial stiffness (via cfPWV) in age-matched T2D men and women, and to what degree these differences are related to augmented oxidative stress, inflammation and endothelial dysfunction. Hypothesis: The relationship between arterial stiffness and elevations in SUA/augmented oxidative stress/endothelial dysfunction/increased inflammatory marker activity seen in T2D women will be weaker or absent in men.

Aim 2: To assess whether XO inhibition is superior to dietary-induced SUA reduction in ameliorating arterial stiffness in T2D subjects. Hypothesis: Although we expect XO inhibition to have the greatest impact, we posit that SUA reduction by either strategy will lead to more improvement in endothelial function and stiffness.

As shown in **Figure 6**, this project has three parts and each subject will participate in only one part. These separate treatment arms are combined into one IRB protocol because they will test an integrated hypothesis regarding uric acid and arterial stiffness in a similar population with identical procedures.

Part 1: Diet treatment

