Medications for glucose control (insulin, metformin, gliptins, GLP-1 agonists, sulfonylureas, sodium glucose co-transporter inhibitors), antihypertensives, hormone replacement therapy, antidepressants, anticoagulants, or statins, will be considered during recruitment, analyses (e.g., using covariate analysis) and interpretation.

Exclusion criteria for hypocaloric low-fructose diet intervention (part 3):

- 1) Habitual diet containing low amount of sugars < 5% of total energy intake
- 2) Recent CVD event (stroke, heart failure hospitalization, revascularization or acute coronary event in the last 12 months), abnormal thyroid tests or chronic liver disease, stage IV renal disease (GFR <30) and hyperparathyroidism.
- 3) Use of azathioprine
- 4) Active cancer
- 5) Autoimmune diseases
- 6) Excessive alcohol consumption (>14 drinks/week for men, >7 drinks/week for women)
- 7) Current tobacco use
- 8) Bodyweight change $\geq 10\%$ within the last 6 months
- 9) History of gout or uncontrolled hypertension
- 10) Pregnancy or lactation in women (or women not using contraceptives)

Medications for glucose control (insulin, metformin, gliptins, GLP-1 agonists, sulfonylureas, sodium glucose co-transporter inhibitors), antihypertensives, hormone replacement therapy, antidepressants, anticoagulants, or statins, will be considered during recruitment, analyses (e.g., using covariate analysis) and interpretation.

VI. NUMBER OF SUBJECTS

Sample size calculations are based primarily on satisfying the requirements of Aim 2, i.e. to show that XO inhibition and fructose restriction reduce PWV, and that these interventions are more effective in women than in men. Calculations are based on the paired *t*-test for pre- to post-treatment change, and independent *t*-tests for comparisons between treatment arms. In both cases, we assume an alpha of .05 and a two-sided alternative.

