The sample size calculations shown in **Table 2** are derived from the literature as follows: De Angelis *et al* have shown that in men, T2D does not increase PWV in age- and BMI-matched men without T2D ³². By contrast, in women, T2D significantly increases PWV compared to women without T2D and importantly, compared to men with T2D. Any reduction in PWV represents a significant reduction in cardiovascular risk ⁷. However, with 6 months of allopurinol treatment, we have chosen a sample size to be able to detect a reduction in PWV of 0.6 m/s, which Ng *et al* showed to be clinically meaningful ⁶⁸. Nine subjects per group (9 men and 9 women) completing the allopurinol arm will allow for 90% power to detect a change of 0.6 m/s and seven subjects/group will allow for 80% power to detect this change **Table 2**. With regard to fructose restriction, our preliminary

Treatments	Power	Alpha	Change PWV	SE of Δ in PWV	# of subjects
Allopurinol	90%	0.05	0.6 m/s	0.4 m/s	9
	80%	0.05	0.6 m/s	0.4 m/s	7
Low-fructose	90%	0.05	0.5 m/s	0.4 m/s	13
	80%	0.05	0.5 m/s	0.4 m/s	10

Table 2

data demonstrate a significant improvement in PWV only in the females. We anticipate that the reduction in PWV with diet may be smaller than that with allopurinol. We would need 13 subjects/group to detect a 0.5 reduction in PWV with 90% power; 10/group would give 80% power. Further, as we do not expect changes in the PWV during 6 month of follow up in the placebo group and to accommodate variability in response and potential dropout, we will include 40 subjects in the low-fructose intervention, 40 subjects in the allopurinol cohort and 20 in the placebo group (half men and half women for all the cohorts). Further and based in our previous weight loss/dietary intervention⁶⁹, we have chosen a sample size to be able to detect a reduction in PWV of 0.6 m/s of 20 diabetic males and 20 diabetic females.

VII. STUDY PROCEDURES/ DESIGN/TREATMENT PLAN

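### Table 2 labels 0.4 m/s an SE but uses it as an SD, ties no row to a test, and at SD 0.4 its power figures fit neither test named; the sex and drug-diet contrasts have no stated power

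*Combined protocol and SAP*

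**What the plan says.** Section VI sets two-sided alpha at 0.05 and names two tests for the whole section: "Calculations are based on the paired *t*-test for pre- to post-treatment change, and independent *t*-tests for comparisons between treatment arms". It says that the sizes mainly serve Aim 2, which it describes as "to show that XO inhibition and fructose restriction reduce PWV, and that these interventions are more effective in women than in men". Section I.B words Aim 2 differently: "To assess whether XO inhibition is superior to dietary-induced SUA reduction in ameliorating arterial stiffness in T2D subjects".

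For allopurinol, nine per group (spelled out as nine of each sex) "completing the allopurinol arm will allow for 90% power to detect a change of 0.6 m/s and seven subjects/group will allow for 80% power". For the low-fructose diet, "We would need 13 subjects/group to detect a 0.5 reduction in PWV with 90% power; 10/group would give 80% power". Table 2 repeats these four cases. Its variability column is headed "SE of Δ in PWV" and reads 0.4 m/s in every row. It has no column for the test or the contrast.

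Enrolment is then set at 40 low-fructose, 40 allopurinol and 20 placebo, half of each sex, plus 20 men and 20 women on the hypocaloric diet. Section III.A allows for 10% dropout. No power is given at any of these sizes.

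**The concern.** The SE of a mean change shrinks as n grows, so one SE cannot hold at n = 7, 9, 10 and 13. Either the label is wrong or the input is. The documents say that the calculations come from the literature, but they attach no source to 0.4.

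The rows also cannot be matched to a test. A group of nine men and nine women fits a paired change within each sex, and it equally fits a comparison of men with women. The two readings give quite different power from the same inputs.

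These are the only power figures in the protocol. As they stand, a reader cannot tell which question they answer, or what the enrolled numbers can show for the two contrasts that Section VI and Aim 2 put forward.

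**Working it through.** **Inputs.** Alpha 0.05 two-sided; changes of 0.6 and 0.5 m/s; 0.4 m/s; n = 9, 7, 13, 10 (Section VI and Table 2); 10% dropout (Section III.A). Four-part figures follow Table 2's row order: 0.6 m/s at 90% and 80%, then 0.5 m/s at 90% and 80%.

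**1. Reproducing the printed n.** The two-sample normal formula with SD 0.4 is n per group = 2(z₀.₉₇₅ + z_power)² × SD²/δ².
- 0.6 m/s: 2 × 10.507 × 0.16/0.36 = 9.34 and 2 × 7.849 × 0.16/0.36 = 6.98
- 0.5 m/s: 2 × 10.507 × 0.16/0.25 = 13.45 and 2 × 7.849 × 0.16/0.25 = 10.05

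Rounded to nearest, these are the printed 9/7/13/10.

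**2. Taking the label literally.** With SE = 0.4 the standardised effect is 0.6/0.4 = 1.5 or 0.5/0.4 = 1.25, whatever n is. Power by paired t (n − 1 df) is about 26/24/21/20%; by normal approximation it is 32% or 24%. Neither is near 80–90%. If 0.4 is an SD, the SE of a mean change is 0.4/√n = 0.13/0.15/0.11/0.13 m/s.

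**3. Exact power at the printed n, SD 0.4.** Noncentral t, with noncentrality δ/(SD√(2/n)) on 2n − 2 df for the independent test and δ√n/SD on n − 1 df for the paired test. For the first row these are 0.6/(0.4 × 0.471) = 3.18 on 16 df and 0.6 × 3/0.4 = 4.5 on 8 df.

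| Row | Stated n, power | Independent t: power; n needed | Paired t: power; n needed |
|---|---|---|---|
| 0.6 m/s | 9, 90% | 84.8%; 11 | 97.5%; 7 |
| 0.6 m/s | 7, 80% | 73.1%; 9 | 90.8%; 6 |
| 0.5 m/s | 13, 90% | 86.4%; 15 | 98.5%; 9 |
| 0.5 m/s | 10, 80% | 75.3%; 12 | 93.9%; 8 |

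The stated figures are too high under one named test and too low under the other.

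**4. Effect of rounding in 0.4.** An exact independent t-test returns all four printed n if the SD was about 0.361–0.368, which also prints as 0.4. At 0.365 its power is 90.5/80.6/91.8/82.5%.

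**5. Enrolled sizes at SD 0.4, before and after 10% dropout.**

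| Contrast | Sizes | Result |
|---|---|---|
| Paired change within sex, 0.6 or 0.5 m/s | 20; 18 | over 99% at both |
| Allopurinol v placebo, pooled, 0.6 m/s | 40 v 20; 36 v 18 | over 99.9%; 99.9% |
| Allopurinol v placebo within sex, 0.6 m/s | 20 v 10; 18 v 9 | 96%; 94% |
| Men v women within an arm | 20 v 20; 18 v 18 | 80% power for 0.36; 0.38 m/s |
| Drug v diet | 40 v 40; 36 v 36 | 80% power for 0.25; 0.27 m/s |

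**6. If 0.4 were a published SE (assumption).** For a mean change in m people, SD = 0.4√m; m is unknown. Pooled allopurinol v placebo would have 97% power at m = 2 and about 87% at m = 3 (95% and 84% after dropout), falling below 80% from m = 4 (SD 0.8: 77%, 72%). Within sex it would be below 80% from m = 2 (75%, 70%).

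**The case against.** The strongest reply is that nothing here changes enrolment. Each active arm takes 20 per sex, 18 after dropout, which exceeds the t-corrected 11/9/15/12. Section VI says that the numbers were raised to allow for variable response and dropout. That stands: the t correction alone does not make the trial too small.

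A reader might also infer from step 1 that the t correction was certainly left out. The documents do not prove it. Step 4 shows that an unrounded SD gives the same n by an exact test. A paired normal formula with an SD of change of 0.4√2 = 0.566 also gives the same 9.34/6.98/13.45/10.05. The omission is likely, not established.

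A reader might take 0.6 − 0.5 = 0.1 m/s as the planned drug-diet difference and report 20% power (18% after dropout; 253 per group for 80%). Section VI says only "We anticipate that the reduction in PWV with diet may be smaller than that with allopurinol". The 0.6 and 0.5 are separate changes to detect, and no target for their difference is stated. The 20% is a consequence of an assumption, not the plan's own figure.

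Finally, that a published SE was entered as an SD is only a possibility; step 6 shows what would follow. What survives all of this is the label, the missing source, the rows without a test, and the silence on two named contrasts.

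**Conclusion.** The point holds in this form. The SE label is wrong as written, because 0.4 yields the printed sizes only as an SD. At SD exactly 0.4 the stated powers are 3.6 to 6.9 points too high for an independent t-test (90 − 86.4; 80 − 73.1) and 7.5 to 13.9 points too low for a paired one (97.5 − 90; 93.9 − 80). Neither men v women nor drug v diet has a target difference or a power, although Section VI and Aim 2 name them.

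It should not be read as showing an undersized trial. If the SD is 0.4, the paired change and the randomised comparison with placebo are well covered. The two contrasts without a stated power are covered only for differences of about 0.36–0.38 m/s (sex, within an arm) and 0.25–0.27 m/s (drug v diet). All of this rests on the SD being 0.4. If that figure is a published SE, adequacy cannot be judged until it is converted.

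**What to change.** Revise Section VI and Table 2:

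1. Relabel 0.4 as the SD of the within-person change in PWV, with its unrounded value and source. If it is a published SE, convert it and recompute.
2. Name the test and contrast for each row.
3. Restate n or power from the t distribution for that test. At SD 0.4 the values are those in the step 3 table.
4. State power or the detectable difference at the enrolled sizes, before and after 10% dropout, for the five contrasts in step 5, including the pooled comparison with placebo. If a 0.1 m/s drug-diet difference is shown, mark it as an assumption, and do not describe that contrast as powered for small differences.
5. Give the SD and power behind the hypocaloric arm's 20 per sex, which has a 0.6 m/s target but no row in Table 2.

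The cost is text and one table; no extra patients are proposed. The downside is that some stated figures become less favourable. If 0.4 proves to be an SE, the sponsor must also decide whether the enrolled sizes still serve the aims.

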Following screening, eligible male and female subjects will be assigned to one of the three treatment arms. In the medication arm of the study, they will be randomized to either the allopurinol group (n=40; 20 men and 20 women), or the placebo (n=20; 10 men and 10 women) for 6 months, with a final drug/placebo allocation ratio of 2:1 using a permuted block design with random variation of block size. In the isocaloric low-fructose arm of the study, 20 women and 20 men will be recruited to enter a dietary treatment of fructose restriction for 6 months. In the hypocaloric low-fructose arm of the study, 20 women and 20 men will be recruited to enter a dietary treatment of calorie and fructose restriction for 6 months.

A. Screening/Initial Consenting Visit

The first visit to the CRC will take approximately 6 hours and include a written consent to be screened. The subject is instructed to hold their glucose lowering AM medications (subject will resume regular medications after blood has been drawn), and not to eat or drink anything besides water for at least 10 hours before this visit. The subject is also told not to exercise the morning of this visit. After signing the screening consent form, medical information is obtained by the study team, including: DOB, gender, ethnic/racial category, height, body weight (history of body weight gain or

[figure not shown]

Figure 8. Order of events at the Screening Visit occurring at the clinical research center (CRC).

loss), waist circumference, vitals, and a medical history questionnaire. A fasting blood draw is taken to test for biochemistries. Subjects will also undergo a DEXA scan and vascular measurements including carotid intima media thickness (cIMT), carotid femoral pulse wave velocity (cfPWV), Glycocheck, Near-Infrared Spectroscopy (NIRS), Brachial artery FMD, popliteal artery FMD testing, and OGTT with femoral artery blood flow (**Figure 8**).

An introduction to the clinical trial will be done which includes abbreviated descriptions of the various treatment arms and the placebo arm (no treatment). As soon as the blood biochemistry results are available, the subject is contacted, provided with a copy of the results. If eligible for the allopurinol/placebo arm or (isocaloric) low fructose diet intervention arm, study staff discuss with him/her whether they would like to be consented for enrollment in one of the present studies.

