Subjects that are ineligible for both the allopurinol/placebo and (isocaloric) low fructose arms or do not want to pursue the 6-month intervention will be offered the opportunity to participate in the hypocaloric low fructose arm. Participants that have previously failed initial screening (were ineligible to participate in arm 1 or 2 of the study) will be offered the opportunity to re-consent to the study and have vascular measurements taken at an additional paid screening visit and to enroll in the 5-month long hypocaloric low fructose arm (arm 3).

B. Baseline/Formal Consenting Visit

The subject will arrive to the CRC in the morning to perform further metabolic and vascular tests (**Figure 9**). The subject is instructed to hold their glucose lowering AM medications (subject will resume regular medications after the visit has been completed), and not to eat or drink anything besides water for at least 10 hours before this visit. The subject is also told not to exercise the

[figure not shown]

Figure 9. Order of events at the Baseline Visit occurring at the clinical research center (CRC).

morning of this visit. The visit will take up to 8 hours and the subjects must be fasted. Upon arrival, the participant meets with one of the study's physicians to review and sign the study consent forms. The subject then voids and the study staff takes anthropometric measurements and repeats a DEXA scan at the discretion of the investigator. Subjects will then be placed supine in a quiet, climate-controlled room (22–23 ° C) to rest before vascular measurements are repeated by study staff, including: cIMT, PWV, Glycocheck, FMD and NIRS. Vital signs are measured and an IV line is placed in each arm by the nurse in order to draw blood and infuse during a hyperinsulinemic-euglycemic clamp. The CRC vascular procedures will be repeated again at interim and final visits at 3 and 6 months.

C. Interim visit

An interim visit will include fasting blood draws. Study staff will assess blood pressure, heart rate, weight, and waist circumference as well as body composition (DEXA), cIMT, FMD, NIRS, Glycocheck, and cfPWV. This visit will take up to 4 hours and must occur in the fasting state.

D. Final visit

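### The vascular measures are taken twice before treatment, but the plan neither defines the pre-treatment value nor uses both readings; pre-specify it, using both in the allopurinol–placebo comparison

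*Combined protocol and SAP*

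**What the plan says.** The screening visit (section VII.A) includes "vascular measurements including carotid intima media thickness (cIMT), carotid femoral pulse wave velocity (cfPWV), Glycocheck, Near-Infrared Spectroscopy (NIRS), Brachial artery FMD", and also popliteal FMD. At the baseline visit (section VII.B) subjects are placed supine in a climate-controlled room "to rest before vascular measurements are repeated by study staff, including: cIMT, PWV, Glycocheck, FMD and NIRS". Both visits precede treatment. One set follows at 3 months and one at 6 months.

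The tests for PWV are named only in section VI: "Calculations are based on the paired *t*-test for pre- to post-treatment change", and independent t-tests "for comparisons between treatment arms"; for both, "we assume an alpha of .05 and a two-sided alternative". Table 2 lists 0.4 m/s under "SE of Δ in PWV". The text states that nine per group on allopurinol "will allow for 90% power to detect a change of 0.6 m/s and seven subjects/group will allow for 80% power". For the diet it says: "We would need 13 subjects/group to detect a 0.5 reduction in PWV with 90% power; 10/group would give 80% power".

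Section I.B refers to measurements before, during and after treatment without saying which pre-treatment reading counts. Section VII.D has the final visit repeat all baseline measurements. That points towards the baseline visit but does not define the value to be analysed.

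**The concern.** Each duplicated measure has two candidate pre-treatment readings and no rule for choosing between them. Screening, baseline or their mean could each be selected once results are known, and each would give a somewhat different change score.

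The second issue is precision. Groups are small: 20 per sex in each active arm and 10 per sex on placebo. Noise in a single pre-treatment reading passes into every change score and weakens every baseline covariate. The second reading is already collected. Entry does not depend on any vascular value (section V), so using the screening reading brings no selection-driven regression to the mean. Serum uric acid differs: Parts 1 and 2 exclude screening values below 5.5 mg/dL, so a high screening value is partly selected noise.

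**Working it through.** **Inputs from the protocol.** Two-sided alpha 0.05; differences of 0.6 m/s (allopurinol) and 0.5 m/s (diet); 0.4 m/s for the variability of the change; planned groups of 40 allopurinol, 20 placebo and 40 isocaloric diet, half of each sex; 10% dropout. **Assumptions.** All correlations, the share of variance that is visit-to-visit noise, a 0.3 m/s sex difference, SDs above 0.4, and equal variances across visits.

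**1. Table 2 reproduced.** n per group = 2 × [SD × (z_α/2 + z_power) / d]², with SD 0.4 and z sums of 3.242 (90%) and 2.802 (80%):
- d = 0.6: 2 × (0.4 × 3.242/0.6)² = 9.34 and 2 × (0.4 × 2.802/0.6)² = 6.98 (stated 9 and 7)
- d = 0.5: 13.45 and 10.05 (stated 13 and 10)

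So 0.4 works as an SD although Table 2 labels it SE. The figures match the two-sample formula; a paired t-test would give 7, 6, 9 and 8.

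**2. Change scores, exchangeable visits.** Let r be the common correlation and s² the variance at one visit.
- One reading: 2s²(1 − r)
- Mean of two: s² + s²(1 + r)/2 − 2rs² = 1.5s²(1 − r)

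The ratio is 0.75. If all of 0.4² = 0.16 is visit-to-visit noise, the variance falls to 0.12 (SD 0.346). If half of it is true difference in response, it falls to 0.08 + 0.75 × 0.08 = 0.14 (SD 0.374), a 12.5% cut. The ceiling is 25%.

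**3. ANCOVA, exchangeable visits.** Residual variance is proportional to 1 − r² with one reading and 1 − 2r²/(1 + r) with the mean of two.

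| r | one | mean of two | cut |
|---|---|---|---|
| 0.5 | 0.750 | 0.667 | 11% |
| 0.7 | 0.510 | 0.424 | 17% |
| 0.8 | 0.360 | 0.289 | 20% |
| 0.9 | 0.190 | 0.147 | 22% |

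**4. Visits not exchangeable.** Take baseline–final r = 0.8 and screening–baseline r = 0.9, and vary screening–final r. The entries are variance relative to the baseline reading alone. For both readings as separate covariates, R² = (r₁² + r₂² − 2r₁r₂r₁₂)/(1 − r₁₂²).

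| screening–final r | change score, mean | ANCOVA, mean | ANCOVA, both readings |
|---|---|---|---|
| 0.80 | 0.875 | 0.906 | 0.906 |
| 0.75 | 1.000 | 1.022 | 0.987 |
| 0.70 | 1.125 | 1.133 | 0.994 |

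The mean can lose precision. Entering both readings as covariates does not, apart from one degree of freedom.

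**5. What it buys.** Power = Φ[d/(SD√(1/n₁ + 1/n₂)) − 1.96], with the SD of change; the best case multiplies SD by √0.75.
- Placebo 20 v allopurinol 40, d = 0.6, SD 0.4: above 99% with one reading, and still above 99% at 18 v 36 after dropout.
- Same contrast at assumed SD 0.8: 78% to at most 89%. At SD 1.0: 59% to at most 72%.
- Men v women within an active arm, 20 v 20, assumed 0.3 m/s, SD 0.4: 66% to at most 78% (64% to 76% by the t distribution).
- Sex-by-drug contrast, detectable at 80% power: 2.802 × 0.4 × √(1/20 + 1/20 + 1/10 + 1/10) = 0.61 m/s, falling to 0.57 (half-noise case) or 0.53 (best case).

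**6. Uric acid.** Regression to the mean = (1 − repeatability) × mean excess above the population mean, given selection at 5.5 mg/dL. With an assumed population mean of 5.5–6.0, SD 1.4 and repeatability 0.8–0.9, it is about 0.08–0.22 mg/dL. None of these three inputs is in the protocol.

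**The case against.** The strongest reply is that the plan makes no wrong choice here. A reader might infer that it commits to a single reading and throws the other away. It does not say so: a paired t-test is compatible with a mean of two readings. What stands is that the value is undefined.

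A reader might also infer that the two visits are identical in preparation, so that averaging is free. The fasting, exercise and held-medication instructions do match. But at screening regular medication resumes after the blood draw, and at baseline only after the visit. Supine rest in a climate-controlled room is described only at baseline. The screening visit also contains an OGTT, and the figures giving the order of events are not available. Screening at Day −30 appears only in the allopurinol dosing table, with no gap stated for the diet parts. Section VII.A provides an additional screening visit, with vascular measurements, for people who failed an earlier one, so it is unclear whether every subject has two comparable sets. These points stand; exchangeability is an assumption.

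The diet arms have no concurrent control: section VII.K says those subjects serve as their own. A first-visit effect on cfPWV would enter an averaged pre-treatment value and bias the pre–post change. In the randomised comparison it would be shared by both groups. This objection stands and limits where averaging should be primary.

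Finally, on the plan's own figures power for 0.6 m/s is already ample. That is true if 0.4 is the right SD.

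**Conclusion.** The concern holds in a limited form. Two pre-treatment sets are collected, the value to be analysed is undefined, and no analysis uses both. Pre-specifying it is worth doing whichever reading is chosen. Using both readings is a modest gain in precision for the randomised comparison: about 11–22% of residual variance under ANCOVA for r between 0.5 and 0.9 with exchangeable visits, and at most 25% for change scores. These figures rest on assumed correlations, and the gain can vanish or reverse for a simple mean if screening tracks the final value less well.

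The practical effect is negligible for 0.6 m/s at SD 0.4, and useful for smaller sex contrasts or a larger SD. The SE label in Table 2 leaves that SD uncertain.

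The documents do not support the broader inference that averaging would sharpen every comparison at no cost. The clamp with contrast-enhanced ultrasound has only one pre-treatment value, and in the diet arms averaging carries a possible bias.

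**What to change.** Add a short definition of the pre-treatment value to the analysis plan:

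- **Allopurinol versus placebo:** ANCOVA of the final value on the pre-treatment measure, for each duplicated vascular outcome, using the mean of the screening and baseline readings or both as separate covariates. Separate covariates are safer if the visits are not well matched.
- **Missing or remote screening:** use the baseline visit alone when screening is absent or falls outside a stated maximum gap. For re-screened subjects, state which screening counts.
- **Uncontrolled diet arms:** keep the baseline-visit value as the main pre-treatment value for pre–post change. Check for a systematic screening-to-baseline shift, then report the two-visit mean as a sensitivity analysis.
- **Serum uric acid, Parts 1–2:** take the pre-treatment value from the baseline visit, and confirm that uric acid is assayed in that sample.
- **Clamp with contrast-enhanced ultrasound:** no change.

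The paired readings also give the trial's own short-term repeatability for cfPWV and FMD, a useful check on the 0.4. The cost is a paragraph of text and a little analysis time, with no new vascular test, visit or subject. The remaining downside is that the gain in precision is not guaranteed.
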